The purpose of MNA is to detect the presence of undernutrition and the risk of developing undernutrition among the elderly in home-care programmes, nursing homes and hospitals. The prevalence of undernutrition among the elderly may reach significant levels (15–60%) under these circumstances (8). The screening methods mentioned above will detect undernutrition among many elderly patients, but for the frail elderly the MNA screening is more likely to identify risk of developing undernutrition, and undernutrition at an early stage, since it also includes physical and mental aspects that frequently affect the nutritional status of the elderly, as well as a dietary questionnaire. It is in fact a combination of a screening and an assessment tool, since the last part of the form (not reproduced here) is a more detailed exploration of the items in the first part of the form.

Evaluation. The predictive validity of MNA has been evaluated by demonstrating its association with adverse health outcome (9), social functioning (10), mortality (11, 12) and a higher rate of visits to the general practitioner (13). In a randomized trial of elderly at risk according to MNA, those given oral supplements increased body weight, but not grip strength (14), and in another similar (but small) randomized trial of elderly in a nursing home, the intervention group increased dietary intake but no functional or clinical outcome data were reported (15). The content validity has not been reported. The reliability (inter-observer variation) was estimated, with a $\kappa = 0.51$ (8). The MNA takes <10 min to complete and its practicability has been shown by its use in a large number of studies, see (8).

Children

A universally accepted screening tool for children is not yet available (although guidelines are in preparation under the Chairmanship of [name], Munich). It is already standard practice among paediatricians to maintain height and weight charts, allowing calculation of growth velocity which is high-sensitive to nutritional status. Pubertal development is also impaired during undernutrition.

Other screening systems

In their recent guidelines, the ASPEN board of directors stated that no screening system has been validated with respect to clinical outcome (16). They also suggested that,

in the absence of an outcomes validated approach, a combination of clinical and biochemical parameters should be used to assess the presence of malnutrition. They suggest using the subjective global assessment, SGA (17), which classifies patients subjectively on the basis of data obtained from history and physical examination, since this system has been validated in several ways other than with respect to clinical outcome, e.g. inter-observer variation. However, the lack of a direct connection between the observations and the classification of patients leaves the tool more complex and less focused than desired for rapid screening purposes.

An analysis of a total of 44 screening tools for use in hospital and the community (3) indicated that tools were published with insufficient details regarding their intended use and method of derivation, and with an inadequate assessment of their effectiveness. No one tool satisfied a set of criteria regarding scientific merit. The present recommendations by ESPEN may share some of these short-comings, but in view of the massive neglect of nutritional problems in health institutions, and the explicit lack of generally accepted screening tools, the predictive validity given above is considered sufficient to provide a practical and reasonable approach in the light of present knowledge. These recommendations may need to be modified in the light of future experience.

Predictive validity vs meta-analyses of treatment

The predictive validity reported here needs to be commented upon in relation to recent meta-analyses, or systematic reviews. Such analyses suggest that nutritional support by the enteral or oral route improves functional capacity and clinical outcome, and reduces length of stay and mortality, e.g. (18, 19). In a recent meta-analysis of studies employing parenteral nutrition (20), it was pointed out that there are inadequate data to assess the efficacy of parenteral nutrition in patients who are severely undernourished, who have highly catabolic disease processes, or who cannot be provided with enteral nutrition for several weeks. These are in fact the patients who most commonly receive supportive parenteral nutrition now-a-days, and for ethical reasons, there will probably not be randomized trials available in the future either. The majority of studies available deal with the grey area of patients who are less undernourished/not undernourished and/or are mildly-moderately catabolic. With these studies at hand, it was difficult to identify clinical conditions where parenteral nutrition would be clinically effective (20). However, the literature analysis mentioned above (4) suggests that parenteral nutrition is clinically effective in studies of patients who rather more than just fulfill the criteria for being nutritionally at risk.

Furthermore, nutrients known to be essential for healthy humans are also essential for patients, and therefore the required documentation is not to confirm

[figure not shown]
the essentiality of nutrients among patients, but rather to define when a certain form of nutritional support is more beneficial than leaving the patient to develop nutritional deficiencies. Therefore, meta-analyses and systematic reviews of nutritional support are too simplistic, if performed by analogy with treatment using a new drug. Finally, a nutritional care plan in most cases will involve food, oral supplements, tube feeding and parenteral nutrition, often used interchangeably in the same patient, whereas the majority of randomized trials, and meta-analyses, have dealt with studies of single modality treatments. The predictive validity of a screening tool therefore cannot be directly based on meta-analyses available at present.

References

Appendix

Malnutrition Universal Screening Tool (MUST) for adults

Can be adapted for special circumstances (e.g. when weight and height cannot be measured or when there are fluid disturbances) using specified alternative measurements including subjective criteria. It also identifies obesity (BMI > 30 kg/m²).

Nutritional Risk Screening (NRS 2002)

Table 1 Initial screening			
		Yes	No
1	Is BMI <20.5?		
2	Has the patient lost weight within the last 3 months?		
3	Has the patient had a reduced dietary intake in the last week?		
4	Is the patient severely ill? (e.g. in intensive therapy)		
Yes: If the answer is 'Yes' to any question, the screening in Table 2 is performed. No: If the answer is 'No' to all questions, the patient is re-screened at weekly intervals. If the patient e.g. is scheduled for a major operation, a preventive nutritional care plan is considered to avoid the associated risk status.			

Table 2 Final screening			
Impaired nutritional status		Severity of disease (≈ increase in requirements)	
Absent Score 0	Normal nutritional status	Absent Score 0	Normal nutritional requirements
Mild Score 1	Wt loss >5% in 3 mths or Food intake below 50-75% of normal requirement in preceding week	Mild Score 1	Hip fracture*, Chronic patients, in particular with acute complications: carthrosis* , COPD* , Chronic hemodialysis, diabetes, oncology
Moderate Score 2	Wt loss >5% in 2 mths or BMI 18.5 – 20.5 + impaired general condition or Food intake 25-60% of normal requirement in preceding week	Moderate Score 2	Major abdominal surgery* Stroke* Severe pneumonia, hematologic malignancy
Severe Score 3	Wt loss >5% in 1 mth (>15% in 3 mths) or BMI <18.5 + impaired general condition or Food intake 0-25% of normal requirement in preceding week in preceding week.	Severe Score 3	Head injury* Bone marrow transplantation* Intensive care patients (APACHE > 10) .
Score:	+	Score:	=Total score
Age	if ≥ 70 years: add 1 to total score above		=age-adjusted total score
Score ≥3: the patient is nutritionally at-risk and a nutritional care plan is initiated Score <3: weekly rescreening of the patient. If the patient e.g. is scheduled for a major operation, a preventive nutritional care plan is considered to avoid the associated risk status.			

NRS-2002 is based on an interpretation of available randomized clinical trials.

*indicates that a trial directly supports the categorization of patients with that diagnosis. Diagnoses shown in *italics* are based on the prototypes given below.

Nutritional risk is defined by the present **nutritional status** and risk of impairment of present status, due to **increased requirements** caused by stress metabolism of the clinical condition.

A **nutritional care plan** is indicated in all patients who are

(1) severely undernourished (score = 3), or (2) severely ill (score = 3), or (3) moderately undernourished + mildly ill (score 2 + 1), or (4) mildly undernourished + moderately ill (score 1 + 2).

Prototypes for severity of disease
Score = 1: a patient with chronic disease, admitted to hospital due to complications. The patient is weak but out of bed regularly. Protein re-

quirement is increased, but can be covered by oral diet or supplements in most cases.

Score = 2: a patient confined to bed due to illness, e.g. following major abdominal surgery. Protein requirement is substantially increased, but can be covered, although artificial feeding is required in many cases.

Score = 3: a patient in intensive care with assisted ventilation etc. Protein requirement is increased and cannot be covered even by artificial feeding. Protein breakdown and nitrogen loss can be significantly attenuated.

Initial Screening in Mini Nutritional Assessment (MNA[®]) for the elderly

A	Has food intake declined over the past 3 months due to loss of appetite, digestive problems, chewing or swallowing difficulties? 0 = severe loss of appetite 1 = moderate loss of appetite 2 = no loss of appetite		
B	Weight loss during last months? 0 = weight loss greater than 3 kg 1 = does not know 2 = weight loss between 1 and 3 kg 3 = no weight loss		
C	Mobility? 0 = bed or chair bound 1 = able to get out of bed/chair but does not go out 2 = goes out		
D	Has suffered physical stress or acute disease in the past 3 months? 0 = yes 2 = no		
E	Neuropsychological problems? 0 = severe dementia or depression 1 = mild dementia 2 = no psychological problems		
F	Body Mass Index (BMI) [weight in kg]/[height in m] ² 0 = BMI less than 19 1 = BMI 19 to less than 21 2 = BMI 21 to less than 23 3 = BMI 23 or greater		
Screening score (total max. 14 points)			
12	points or greater	Normal—not at risk → no need to complement assessment	
11	points or below	Possible malnutrition → continue assessment	

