9.5. Endpoints

- Demographic characteristics: Age and ECOG at inclusion, sex, complete physical examination (including blood pressure and heart rate), enolic and smoking habits, other cancer history.
- NET diagnosis: date of initial diagnose, age at diagnose.
- NET at baseline: location of primary tumor, histological grade, TNM grade, Ki-67, mitotic index, metastatic locations, functional status of the tumor.
- NET treatment:
 - a. Prior treatments: systemic therapies for NET (type, start and end date, best response, progression date), locoregional therapies (type, start and end date, best response, progression date), surgery (dates, outcome) and radiotherapy (type, dose, start and end date).
 - b. Current treatments (at baseline): systemic therapies for NET (type, start date, best response), locoregional therapies (type, start date, best response) and radiotherapy (type, dose, start date).
 - c. Hospitalizations (at baseline): cause, start and end date.
- Target nutritional history: regular weight, loss of weight (start date, duration), weekly food intake (calculation of mean daily caloric intake, mean protein intake, (animal and vegetal), mean carbohydrates intake (simple or complex), mean fat intake (saturate, monounsaturated, polyunsaturated, n-3 and n-6), and mean fiber intake (soluble and insoluble). The PREDIMED score test will be used (appendix 2). Calculation of caloric-protein nutritional requirements, according to ESPEN guidelines. Need for supplementation, if necessary, type of oral nutritional supplement (ONS) used, volume administered (ml / day), type of administration regimen (continuous or discontinuous). Number of intakes per day and volume of intakes and existence of intolerance related to enteral nutrition (EN): Diarrhea, constipation, bloating, nausea, vomiting, regurgitation, fever, ...).
- Nutritional screening test: NRS test (nutritional risk screening) (appendix 3) and SGA test (subjective global assessment) (appendix 4). The GLIM criteria for diagnosis and stratification of malnutrition will be applied.

- Quality of life (QoL) test: EORTC QLQ-C30 (European Organisation for Research and Treatment of Cancer Quality of Life Questionnaire)(appendix 5) and the NET specific questionnaire (GI.NET21)(appendix 6).
- Anthropometry: height, weight at baseline, BMI, triceps fold, brachial circumference, abdominal circumference, calf circumference.

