9.8. Data analysis

The study will be analyzed descriptively, using descriptive epidemiological methods as detailed below. All results, including p-values and confidence intervals, are to be interpreted descriptively only.

- The analyses will be performed to the total population included fulfilling all selection criteria.

Additional subgroup analyses may be performed to fulfill secondary objectives (depending on the finally observed number of patients in such subgroups), including but not limited to: Tumor type, stage, grade and functionality, treatment type or survival.

The data will be summarized using the mean (standard deviation) and the median (1st and 3rd quartiles) in the case of continuous variables and using relative and absolute frequencies in the case of categorical variables. The prevalence together with its corresponding 95% confidence interval will be estimated by fitting a binomial model. The associations between the nutritional status and the quality of life of the patients, the stage of the disease and the tumor grade will be contrasted using ordinal regression models. Survival will be analyzed using cox regression models or parametric survival models according to the assumptions that meet the data. All analyzes will be performed using R software (version 4.03 or higher).

The final analysis will be performed within 6 months after the inclusion of the last patient. The final data interpretation and presentation in reports, scientific publications and/or congresses will be done within 12 months after the final analysis. The final report will be presented to the competent authorities 12 months after the end of study.

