APPENDIX 4.**SUBJECTIVE GLOBAL ASSESSMENT (SGA) TEST**

Anexo 2 299

VALORACIÓN GLOBAL SUBJETIVA GENERADA POR EL PACIENTE

Por favor, conteste al siguiente formulario escribiendo los datos que se le piden o señalando la opción correcta, cuando se le ofrecen varias

Nombre y Apellidos _____	Edad _____ años Fecha / /
PESO actual _____ kg Peso hace 3 meses _____ kg	DIFICULTADES PARA ALIMENTARSE: Sí No Si la respuesta era Sí, señale cual / cuales de los siguientes problemas presenta: falta de apetito ganas de vomitar vómitos estreñimiento diarrea olores desagradables los alimentos no tienen sabor sabores desagradables me siento lleno enseguida dificultad para tragar problemas dentales dolor. ¿Dónde? _____ depresión problemas económicos
ALIMENTACIÓN respecto hace 1 mes: como más como igual como menos Tipo de alimentos: dieta normal pocos sólidos sólo líquidos sólo preparados nutricionales muy poco	
ACTIVIDAD COTIDIANA en el último mes: normal menor de lo habitual sin ganas de nada paso más de la mitad del día en cama o sentado	
Muchas gracias. A partir de aquí, lo completará su Médico	
ENFERMEDADES: _____ _____	EXPLORACIÓN FÍSICA: Pérdida de tejido adiposo: Sí. Grado _____ No Pérdida de masa muscular: Sí. Grado _____ No Edemas y/o ascitis: Sí. Grado _____ No Úlceras por presión: Sí No Fiebre: Sí No
TRATAMIENTO ONCOLÓGICO: _____ _____	
OTROS TRATAMIENTOS: _____ _____	
ALBÚMINA antes de tratamiento oncológico: _____ g/dl	
PREALBÚMINA tras el tratamiento oncológico: _____ mg/dl	

VALORACIÓN GLOBAL, teniendo en cuenta el formulario, señale lo que corresponda a cada dato clínico para realizar la evaluación final:

DATO CLÍNICO	A	B	C
Pérdida de peso	<5%	5-10%	>10%
Alimentación	Normal	deterioro leve-moderado	deterioro grave
Impedimentos para ingesta	NO	leves-moderados	graves
Deterioro de actividad	NO	leve-moderado	grave
Edad	65	>65	>65
Úlceras por presión	NO	NO	SI
Fiebre / corticoides	NO	leve / moderada	elevada
Tto. antineoplásico	bajo riesgo	medio riesgo	alto riesgo
Pérdida adiposa	NO	leve / moderada	elevada
Pérdida muscular	NO	leve / moderada	elevada
Edemas / ascitis	NO	leve / moderados	importantes
Albúmina (previa al tto)	>3,5	3'0-3,5	<3,0
Prealbúmina (tras tto)	>18	15-18	<15

VALORACIÓN GLOBAL,

- A: buen estado nutricional
- B: malnutrición moderada o riesgo de malnutrición
- C: malnutrición grave

**VALORACIÓN GLOBAL SUBJETIVA
GENERADA POR EL PACIENTE (VGS-GP)**

HISTORIAL

Identificación del paciente:

A RELLENAR EXCLUSIVAMENTE POR EL PACIENTE

1. Peso:

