Sumando puntos se determinan la pérdida aguda y subaguda de peso. **Subaguda:** si se dispone de los datos de pérdida de peso durante el último mes, añadir los puntos obtenidos a los puntos correspondientes a la pérdida de peso aguda. Sólo incluir la pérdida de peso de 6 meses si no se dispone de la del último mes. **Aguda:** se refiere a los cambios de peso en las últimas dos semanas: añadir 1 punto al marcador de subaguda si el paciente ha perdido peso, no añadir puntos si el paciente ha ganado o mantenido su peso durante las 2 últimas semanas.

Pérdida Peso en 1 mes	Puntos	Pérdida de Peso en 6 meses
10% o superior	4	20% o superior
5 – 9,9%	3	10 – 19,9%
3 – 4,9%	2	6 – 9,9%
2 – 2,9%	2 – 5,9%	
0 – 1,9%	0	0 – 1,9%

Puntuación Total Recuadro 1 = Subaguda + Aguda = 1

TABLA 2.—Criterios de cuantificación de Enfermedad y/o Condiciones

La puntuación se obtiene adjudicando 1 punto a cada una de las condiciones indicadas abajo, que se correspondan con el diagnóstico del paciente:

Categoría	Puntuación
• Cáncer	1
• SIDA	1
• Caquexia Cardiaca o Pulmonar	1
• Úlcera por decubito, herida abierta o fistula	1
• Existencia de Trauma	1
• Edad superior a 65 años	1

Puntuación Total Tabla 2 = B

TABLA 3.—Cuantificación del Estrés Metabólico

La valoración del estrés metabólico se determina mediante una serie de variables conocidas cuya presencia produce un incremento de las necesidades calóricas y proteicas del individuo. Esta puntuación **es aditiva**, de forma que un paciente con fiebre superior a 39 °C (suma 3 puntos) y si está siendo tratado con 10 mg de prednisona de forma crónica (suma 2 puntos más), lo que hace un total de 5 puntos para el paciente en esta sección.

Estrés	Ninguno (0)	Leve (1)	Moderado (2)	Elevado (3)
Fiebre	sin fiebre	37 y < 38 °C	38 y < 39 °C	39 °C
Duración de la Fiebre	sin fiebre	<72 horas	72 horas	>72 horas
Esteroides	sin esteroides	dosis bajas (<10 mg prednisona o equivalente/día)	dosis moderadas (>10 y <30 mg prednisona o equivalente/día)	altas dosis de esteroides (30 mg prednisona o equivalente/día)

Puntuación Total Tabla 3 = B

TABLA 4.—Reconocimiento Físico

El reconocimiento físico del paciente incluye una evaluación subjetiva de tres aspectos de la composición corporal: tejido graso, masa muscular y estatus hidrático.

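### NRS 2002 and the numeric VGS-GP total contain an age point, but section 9.8 specifies no age adjustment and does not say which tool is the nutritional variable

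*Combined protocol and SAP*

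**What the plan says.** - **NRS 2002 (Appendix 3, final screening table).** The total is a nutrition score plus a disease score, followed by an age line: "if ≥ 70 years: add 1 to total score above". The cut-off comes after it: "Score ≥3: the patient is nutritionally at-risk and a nutritional care plan is initiated". The diagnoses listed at disease score 1 include "Chronic hemodialysis, diabetes, oncology".
- **SGA material (Appendix 4).** There are two forms. The first has an age row in its A/B/C table, which reads 65 under A and above 65 under B and C. The second (VGS-GP) gives one point for "Edad superior a 65 años" in its Table 2. That point enters the numeric total A+B+C+D. The A/B/C category on this second form comes from its Table 5, which has no age row.
- **GLIM (9.5).** "The GLIM criteria for diagnosis and stratification of malnutrition will be applied". The documents give no age item for it.
- **Models (9.8; the synopsis repeats this).** The associations of nutritional status with quality of life, stage and grade "will be contrasted using ordinal regression models. Survival will be analyzed using cox regression models or parametric survival models". No covariate is named, and no tool is identified as the nutritional variable. Age is not among the listed subgroups, although that list is open-ended.
- **Available data (9.2.1, 9.5).** Eligibility runs from 18 to 80 years. The collected variables include "Age and ECOG at inclusion, sex".

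**The concern.** In ordinary confounding, nutrition must actually differ by age before age can distort an association. Here the scoring rule creates the link, even if nutrition is identical at all ages. Both thresholds, 65 and 70, lie inside the enrolled age range. A model of survival on NRS risk status with no age term would then report part of the age effect as a nutrition association.

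This bears on the second main hypothesis in section 8, that nutritional status may influence prognosis, survival and quality of life. It also bears on any comparison with the German cross-sectional study cited in section 7, which described malnutrition as an independent prognostic factor. An unadjusted model built on a score that contains age cannot speak to independence.

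**Working it through.** The plan gives no figure on this point, so there is none to reproduce. The check has four steps.

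**1. Can the age point alone change the classification?** Take an oncology patient with disease score 1 and nutrition score 1.
- Age 69: 1 + 1 = 2, not at risk.
- Age 70: 1 + 1 + 1 = 3, at risk.

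Such a patient always reaches the final table. A nutrition score of 1 needs recent weight loss or reduced intake, and either one is a yes in the initial screen.

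**2. How far apart do the age groups move?** These inputs are assumptions, not document figures: disease score 1 for all, 20% with nutrition score 1 and 15% with score 2 or more, the same at every age.
- At risk below 70: 0.15. From 70: 0.15 + 0.20 = 0.35.
- Odds ratio = (0.35/0.65)/(0.15/0.85) = 3.05.
- With 10% at score 1: (0.25/0.75)/(0.15/0.85) = 1.9. With 30%: (0.45/0.55)/(0.15/0.85) = 4.6.

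**3. What does that do to a survival model?** Assume also that 30% are aged 70 or over, that their hazard is HR times that of younger patients, and that nutrition has no effect.
- Share aged 70 or over among at-risk patients: 0.30×0.35/(0.30×0.35 + 0.70×0.15) = 0.50.
- Share among the others: 0.30×0.65/(0.30×0.65 + 0.70×0.85) = 0.25 (rounded).
- Approximate spurious HR at age HR 2.0: (0.50×2 + 0.50)/(0.25×2 + 0.75) = 1.20.
- Low end (10% at score 1, age HR 1.5; shares 0.417 and 0.274): 1.208/1.137 = 1.06.
- High end (30% at score 1, age HR 2.5; shares 0.5625 and 0.217): 1.844/1.326 = 1.39.

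The range is therefore about 1.05 to 1.4.

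A Cox simulation gives the same picture. Each scenario had 20,000 patients aged 18 to 80, mean age parameter 58 to 66 with SD 12 before truncation, nutrition scores 0/1/2/3 in 60/20/12/8% or 50/30/12/8%, disease score 1, two-year follow-up, and no nutrition effect.

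| Age HR per decade | Unadjusted HR for NRS ≥3 |
|---|---|
| 1.0 | 0.99–1.04 |
| 1.3 | 1.04–1.17 |
| 1.6 | 1.11–1.27 |
| 2.0 | 1.21–1.35 |

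With age in the model, the HR is 0.95 to 1.05. With the pre-age score and no age term, it is 0.93 to 1.06 for age HRs of 1.3 to 2.0. Simulation noise is about ±0.05. Age acted log-linearly here, which favours a linear age term.

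**4. How much depends on the disease score?** At disease score 0, a patient with nutrition score 1 reaches only 2 at age 70 and does not cross. The patient who crosses is then the one with nutrition score 2 (2 at 69, 3 at 70). With 12% at score 2 and 8% at score 3:
- At-risk shares are 0.08 below 70 and 0.20 from 70.
- Shares aged 70 or over are 0.06/0.116 = 0.517 among at-risk patients and 0.24/0.884 = 0.271 among the others.
- The approximate HR at age HR 2.0 is 1.517/1.271 = 1.19.

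What matters is how many patients sit one point below the cut-off. If few do, the spurious HR is near 1.

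**The case against.** - **The nutritional variable is not named.** Section 9.8 speaks only of nutritional status, and 9.5 assigns the diagnosis of malnutrition to GLIM. A reader might infer that every measure of nutritional status here contains age. The documents do not support that: no age item is given for GLIM, and the VGS-GP Table 5 rating has none. On the first SGA sheet, age is one row in a subjective overall judgement with no counting rule, so it need not move anyone from A to B. This objection stands and limits the point to NRS and the numeric VGS-GP total.
- **Silence is not exclusion.** A reader might infer that the plan rejects age adjustment. It names no covariates at all. Sections 9.6 and 9.7 refer to a statistical plan, but none is among the documents or listed in Appendix 1. The accurate wording is that no adjustment is specified.
- **Age belongs in NRS.** Appendix 3 says old age is included as a risk factor on the basis of trials in elderly patients. That is a good reason to keep the standard score for prevalence. It does not make an unadjusted association interpretable as nutrition.
- **Results are descriptive, and 10.6 concedes limits on causal interpretation.** This softens the inference but does not change what the score measures. Section 10.6 mentions neither age nor adjustment.
- **Not every outcome is affected.** The documents give no reason why stage, grade or quality of life should vary with age, and without such a relation there is no bias. Survival is the plausible case, yet 9.5 lists no date of death or vital status, so how that analysis will be fed is itself unclear.
- **Disease score 1 for all is doubtful.** The prototype for that score is a patient admitted with complications, and this study also enrols outpatients. That is a fair limit on the size, although step 4 shows that a score of 0 moves the step to other patients and does not abolish it.

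**Conclusion.** The point holds for models that use NRS 2002 or the numeric VGS-GP total. With no age term specified, an association with an age-related outcome will partly reflect age by construction. It is not shown for the VGS-GP Table 5 rating or for GLIM, and is only possible for the first SGA sheet.

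The size cannot be taken from the documents. For NRS of 3 or more, the spurious hazard ratio is about 1.05 to 1.4, given disease score 1, 10% to 30% of patients at nutrition score 1, 30% aged 70 or over and an age hazard ratio of 1.5 to 2.5. It is near 1 if age does not affect the outcome or if few patients sit one point below the cut-off. No corresponding figure was worked out for the numeric VGS-GP total.

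The change should be made because it costs almost nothing and the planned models cannot otherwise separate the two effects. The prevalence estimate is not wrong on this account.

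**What to change.** In section 9.8:

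1. Name the nutritional variable for each ordinal and survival model.
2. Include age at inclusion, as a continuous term, in those models.
3. For models using NRS or the numeric VGS-GP total, add a sensitivity analysis with the score before the age point, and state in advance any cut-off applied to it. A linear age term need not fully absorb a step at 65 or 70, so the covariate alone leaves some overlap. The NRS form already has separate lines for the total and the age-adjusted total; for VGS-GP the age point is removed from box B.
4. Keep the standard NRS score for the prevalence estimate, and also report it below 70 and from 70.

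The cost is one model term and a repeat of the affected association models. Age and all the score components are already on the forms, so no new data are needed.
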